6.1.4 Guidelines for continuation of treatment

Osilodrostat therapy (or matching placebo) is continued unless it must be interrupted or discontinued for safety or other reasons. See [Section 6.3](#) ‘Dose modifications’ for details.

6.1.5 Treatment duration

The treatment duration is 48 weeks in the Core study (Periods 1 and 2), and up to an additional 48 weeks for patients who agree to continue on the optional extension phase. Patients may continue treatment with the study drug until unacceptable toxicity has been experienced, and/or treatment is discontinued at the discretion of the investigator or withdrawal of consent. In the absence of study drug discontinuation, patients will receive osilodrostat for a minimum of 36 weeks to a maximum of 48 weeks during the Core phase.

The optional extension phase will end when all patients who were eligible have transitioned into the long-term safety follow-up study, or were discontinued from the study. Patients must end participation in the optional extension phase within 4 weeks after Protocol Amendment 02 is approved at the site, or by Week 96, whichever occurs first. Patients participating in the optional extension phase between Week 48 and Week 72, and who are eligible, should transition into the long-term safety follow-up study at the next study visit. Patients participating in the optional extension phase between Week 72 and Week 96, and who are eligible, should transition into the long-term safety follow-up study within 4 weeks, at an unscheduled visit if needed, of Protocol Amendment 02 approval at the site.

6.2 Dose titration guidelines

6.2.1 Study Period 1: The double-blind, placebo-controlled period (Weeks 1-12).

For patients on osilodrostat arm, the IE is responsible for study drug dose titrations during Period 1, as the Investigators will not have access to UFC, serum cortisol, and other related laboratory results (as described in [Section 4.1](#)) that could disclose the randomized treatment assignment. The IE will determine the study drug dose once the mUFC level is available from scheduled study visits at Week 2, Week 5 and Week 8, and has access to following data:

- treatment allocation
- mUFC and individual 24-hour UFC values from the most recent study visit (see [Table 7-1a](#)), and mUFC values since the beginning of the trial (as reported by the central laboratory)
- other relevant laboratory data (i.e., serum cortisol, ACTH, and chemistry)
- data on the presence or absence of clinical signs and symptoms of adrenal insufficiency (AI; as recorded on the clinical signs and symptoms of AI eCRF page from the most recent study visit) (see [Section 7.2.2.1.1](#) for details).
- vital signs as recorded in the eCRF
- study drug doses since the beginning of the trial (as recorded on the Drug Administration Record (DAR) eCRF).

In order to maintain the study blind, communication from the IE to the investigator must be limited to communication of study drug dose decisions through the IRT system.

For patients in the placebo arm, a simulated dose titration sequence will be used to maintain the blind.

6.2.1.1 Dose up-titration during Period 1

The initial study drug dose in Period 1 is osilodrostat or placebo 2 mg b.i.d. The dose escalation sequence is: 5 mg b.i.d., 10 mg b.i.d. and 20 mg b.i.d. The IE will up-titrate the osilodrostat dose to the next dose in the sequence, based on the mUFC value until mUFC is normalized. While the goal is to normalize mUFC, decision to up-titrate dose will take into consideration the totality of the data available on each patient e.g. level of mUFC, rate of decrease of mUFC and tolerability of study drug (see [Section 6.3](#)).

Once mUFC is in the normal range (i.e., $mUFC \leq ULN$ and $\geq LLN$), the dose should be maintained, provided there are no safety concerns requiring a dose reduction or interruption (as described below and in [Section 6.3](#)).

6.2.1.2 Dose down-titration during Period 1

The dose of study drug may be down-titrated or interrupted by the IE in patients with mUFC values $< LLN$ or close to LLN together with signs and/or symptoms of adrenal insufficiency. However, it is expected that the investigator will take immediate action to temporarily withhold study medication, without waiting for instructions from the IE, if their patient had suspected adrenal insufficiency, or any AE that requires replacement therapy with glucocorticoids (see

[Section 6.3.1](#) for details). In the event the investigator interrupts study drug, this information must be recorded in the eCRF as soon as possible, so that the IE can take this into account when selecting the next scheduled study drug dose.

6.2.1.3 Intermediate doses for dose adjustment

The preferred doses for either up or down-titration are the standard recommended doses of 2, 5, 10 and 20 mg b.i.d. during Period 1. The preferred intermediate doses are: 3, 7, and 15 mg b.i.d., but other doses may be selected if necessary.

Examples of the appropriate use of intermediate study drug doses are described below:

- A patient previously down titrated from a higher dose for signs and symptoms of adrenal insufficiency to the next lower standard dose (e.g., down titrated from 10 mg b.i.d. to 5 mg b.i.d.), and who experienced an increase in mUFC > ULN, or developed signs and symptoms of hypercortisolism at the lower dose, may be up titrated to an intermediate dose (e.g. 7 mg b.i.d., or, if needed, another intermediate dose between 5 mg and 10 mg b.i.d.) to optimize control.
- A patient who had mUFC > ULN, with or without signs and symptoms of hypercortisolism at one dose, and subsequently had mUFC < LLN or close to the LLN, accompanied by signs and symptoms of hypocortisolism at the next standard higher dose (e.g., after up-titration from 5 mg b.i.d. to 10 mg b.i.d.) may be down titrated to an intermediate dose (e.g., 7 mg b.i.d., or, if needed, other doses between 5 mg and 10 mg b.i.d.) to optimize control.

In patients treated with either osilodrostat or placebo, the study drug could be down-titrated to a dose lower than 2 mg b.i.d., if indicated. In addition, doses of 1 mg b.i.d. or lower can be used, e.g., 1 mg q.d. or 1mg q.o.d. (every other day), if needed for patients that are sensitive to osilodrostat. Importantly, only placebo-treated patients with mUFC < 1.5 x ULN will be down-titrated to doses below 2 mg b.i.d., to avoid unblinding and prolonged hypercortisolism after the Week 12 visit for patients with severely uncontrolled hypercortisolism.

The IEs, investigators, and other site staff should be aware that the use of non-standard doses increases the complexity of dispensing drug to the patient, and self-administration of drug by the patient (see [Section 6.6](#) for details).

6.2.1.4 Communication and implementation of dose changes

As soon as possible (e.g. within 48 hours, if feasible) after the receipt of UFC values for each patient:

1. The IE must determine the next study drug dose (as described in the dosing guidelines, above)
2. The IE must communicate the dose decision for each patient to the corresponding site, through the IRT system in a blinded manner.
3. If a dose change is needed and can be accommodated with the patients' current supplies, the IRT system will provide instructions for the new dose, with the option for this dose change communication to be either via the phone or during an unscheduled visit (per investigator judgment). If a different tablet strength is needed to implement the dose change, the IRT system will recommend that the patient returns to the site (unscheduled

visit) for a dose change. The following need to be completed during both at scheduled and unscheduled site visits:

- a. Patients should return all unused tablets to the site for drug accountability
- b. Patients will receive adequate quantities of medication at the new dose to last until the next scheduled visit.
- c. Patients must receive written instructions regarding the new dose and dosing schedule.

Phone contact: Sites should also initiate a patient contact via the phone approximately 2-5 days after a visit, regardless of whether a dose change was made to assess the following:

1. verify the dose the patient is taking
2. assess the presence or absence of signs and symptoms of adrenal insufficiency or glucocorticoid withdrawal.

Note: If the dose is maintained without change, the patient does not need to return to the site until the next scheduled study visit.

As a general rule, the patient must be on a dose of study medication for at least 4 days before starting a UFC sample collection, in order to ensure that the UFC results reflect adequate exposure to the dose. Therefore, if the time interval between availability of the new dose and next scheduled visit is less than 6 days (when 2 x 24-hour urine collections are required for dose titration) or 7 days (when 3 x 24-hour urine collections are required, e.g. Week 12 visit), patients should not be requested to change their dose until the next scheduled visit when new dosing instructions will be provided and study drug dispensed.

The above guidance is not applicable when urgent dose changes need to be made to ensure patient safety. All study drug dose changes must be documented in the eCRF.

6.2.2 Study Period 2: The single-arm, open-label dose titration period (Weeks 12-48)

Immediately after the Week 12 visit, all patients (in both treatment groups) will receive open-label osilodrostat (as described in [Section 4.1](#)).

Investigators will up-titrate osilodrostat doses to achieve mUFC normalization, according to the following dose escalation sequence: 2 mg b.i.d., 5 mg b.i.d., 10 mg b.i.d., 20 mg b.i.d., and then 30 mg b.i.d.. For any patients on less than 2 mg b.i.d. at the beginning of Period 2, the investigator can increase the dose to 2 mg b.i.d. when the results of the Week 14 visit are available, and then follow the above dose escalation sequence as needed to normalize mUFC. The investigator will follow the same dosing guidelines as described above for the IE ([Section 6.2.1: Study Period 1](#)).

The investigator must remain vigilant to signs and symptoms of adrenal insufficiency and glucocorticoid withdrawal between Week 12 and receipt of the Week 14 UFC results and take appropriate action with regard to the osilodrostat dose, if needed. An unscheduled visit during this time may facilitate assessment of the patient.

Osilodrostat treatment continues until the Week 48 visit with dose-titration to the minimum effective dose that maintains $UFC \leq ULN$. This dose is continued unless a change is required based on mUFC results, or an AE occurs that requires dose reduction or temporarily

withholding osilodrostat. Dose adjustments are to be performed by the investigator as described in the dosing guidelines above for the IE ([Section 6.2.1](#): Study Period 1).

6.2.3 Extension phase (Weeks 48 - 96):

Osilodrostat treatment continues for up to 48 weeks at the established effective dose unless a change is required based on mUFC results, or an AE occurs that requires dose reduction or temporarily withholding osilodrostat. Dose adjustments are to be performed as described for Period 2.

Patients who continue to benefit from treatment during the optional extension phase, have the option to continue treatment on study until any of the following occurs:

- a) they no longer benefit from treatment or
- b) managed access program becomes locally available or
- c) an alternative treatment option becomes locally available or
- d) within 4 weeks after Protocol Amendment 02 is approved at the site, since a separate long term follow up study is now available or by Week 96, whichever comes first. Refer to [Section 6.1.5](#) for details

For patients who transition into a separate long-term study or managed access program, the EOS (last dose + 30 days) visit is not applicable, as treatment on osilodrostat will not be interrupted, and only the EOT visit will be performed.

Those patients who will not continue treatment will complete the EOT extension visit and an EOS (last dose + 30 days) visit, for details of assessments, please refer to [Section 7.1.4](#).

6.3 Dose modifications

6.3.1 Dose modification and dose delay

Please refer to [Section 4.1](#) “Description of study design” and [Section 6.2](#) “Dose titration guidelines” for further information about dose and dosing regimen during various periods of the trial.

In the event of a major safety issue, the investigator may order any laboratory, radiology, or other diagnostic testing required in the safety assessment. In the case of suspected acute adrenal insufficiency or adrenal crisis, the investigator may order and see the results of an urgent serum cortisol level during the double-blind phase of the trial (Weeks 1-12). However, since knowledge of the serum cortisol level could, in effect, unblind the investigator, this action should be reserved for situations in which the clinical diagnosis is in doubt, and the serum cortisol level is considered necessary in the evaluation and treatment of the patient.

For patients who do not tolerate the protocol-specified dosing schedule, dose adjustments are permitted in order to allow the patient to continue the study drug. The following guidelines ([Table 6-1](#) and [Table 6-2](#)) need to be applied. These changes must be recorded in the eCRFs.

Table 6-1 Dose Modification Guidelines for osilodrostat-suspected toxicities

Toxicity	Suggested actions	
	From Week 1 to 12	From Week 12 Onward
	The investigator must immediately inform the IE about AEs and actions taken with study drug by completing the appropriate eCRF.	
Symptomatic adrenal insufficiency See Section 6.3.2 for additional detail.	If the investigator at any time suspects adrenal insufficiency, they can immediately interrupt study drug and initiate replacement with glucocorticoids. Upon recovery as assessed by the investigator*, glucocorticoid therapy can be tapered as tolerated, and study drug can be re-started. The decision to restart study drug will be made by the investigator. The AE and associated treatments with changes to study drug need to be appropriately documented in the eCRF. *Recovery is assessed clinically by the investigator. A general guideline is that glucocorticoid taper can begin when mUFC is in the upper part of the normal range or > ULN, and study drug can be re-started if the patient is clinically stable off glucocorticoid therapy for at least one week, and the mUFC is normal or > ULN. The IE can adjust the dose when sufficient information is provided, i.e., serum cortisol, one or more (up to three) 24-hour UFC result, plasma glucose and electrolytes (as central lab assessment) and completed eCRF pages with clinical signs and symptoms associated with hypocortisolism/adrenal insufficiency event.	
Persistent asymptomatic hypocortisolism (mUFC < LLN) at the lowest dose of osilodrostat (1 mg every other day) See Section 6.3.2 for additional detail.	The IE can interrupt study drug and restart at the same dose as clinically indicated (based on information in the eCRF).	The investigator can interrupt study drug and restart at the same dose as clinically indicated.
Glucocorticoid withdrawal syndrome See Section 6.3.2 for additional detail.	The investigator can interrupt dose until withdrawal symptoms have improved.	The investigator can reduce or interrupt dose until withdrawal symptoms have improved.
*Hypotension (mild, reversible)	The investigator can interrupt dose until blood pressure levels have improved.	The investigator can reduce or interrupt dose until blood pressure levels have improved.
*Hypertension	The investigator can interrupt dose until blood pressure levels have improved; consider ACE inhibitors for treatment of hypertension, or spironolactone as second line treatment, particularly if hypokalemia is present. ACE inhibitors and spironolactone should not be used in combination.	The investigator can reduce or interrupt dose until blood pressure levels have improved; consider ACE inhibitors for treatment of hypertension, or spironolactone as second line treatment, particularly if hypokalemia is present. ACE inhibitors and spironolactone should not be used in combination.
*Weight gain, edema	The investigator can interrupt dose until improved; consider spironolactone for treatment of edema.	The investigator can reduce or interrupt dose until improved; consider spironolactone for treatment of edema.
*Hypokalemia	The investigator can interrupt dose until improved; replace potassium; consider spironolactone or eplerenone for prevention and treatment of hypokalemia	The investigator can reduce or interrupt dose until improved; replace potassium; consider spironolactone or eplerenone for prevention and treatment of hypokalemia

Toxicity	Suggested actions	
	From Week 1 to 12	From Week 12 Onward
	The investigator must immediately inform the IE about AEs and actions taken with study drug by completing the appropriate eCRF.	
*Hyperkalemia	The investigator can interrupt dose until improved; if on spironolactone or eplerenone, reduce or interrupt; treat with kayexalate and other potassium lowering therapies as needed.	The investigator can reduce or interrupt dose until improved; if on spironolactone or eplerenone, reduce or interrupt; treat with kayexalate and other potassium lowering therapies as needed.
*Hirsutism (women only)	The investigator can interrupt dose until improved; review testosterone level; consider treatment with spironolactone, cyproterone acetate or finasteride per local guidelines	The investigator can reduce or interrupt dose until improved; review testosterone level; consider treatment with spironolactone, cyproterone acetate or finasteride per local guidelines
*Acne (women or men)	The investigator can interrupt dose until improved; review testosterone level; consider treatment with spironolactone, cyproterone acetate or finasteride per local guidelines	The investigator can reduce or interrupt dose until improved; review testosterone level; consider spironolactone, cyproterone acetate or finasteride per local guidelines
* Treatment of co-morbidities should be optimized during the screening period and may be considered in these situations and throughout the study treatment period (see Section 6.1.3 for details).		

Instructions for monitoring liver function, and the criteria for withholding, re-initiating, reducing dose or discontinuation of study medication are provided in [Table 6-2](#) below.

Table 6-2 Criteria for interruption and re-initiation of osilodrostat for abnormal liver function

Isolated total Bilirubin elevation	
> ULN – 1.5 x ULN	Maintain dose level
> 1.5 - 3.0 x ULN	Interrupt study drug dose. Monitor LFTs weekly, or more frequently if clinically indicated, until resolved to $\leq 1.5 \times$ ULN: If resolved in ≤ 14 days, restart study drug and maintain dose level If resolved in > 14 days, restart study drug and decrease by one dose level.
> 3.0 - 10.0 x ULN*	Interrupt study drug. Monitor LFTs ^a weekly, or more frequently if clinically indicated, until resolved to $\leq 1.5 \times$ ULN: If resolved in ≤ 14 days, restart study drug and decrease by one dose level. If resolved in > 14 days, then discontinue patient from study drug treatment. The patient should be monitored weekly (including LFTs ^a), or more frequently if clinically indicated, until total bilirubin has returned to baseline or stabilized over 4 weeks.
> 10.0 x ULN*	Discontinue patient from study drug treatment The patient should be monitored weekly (including LFTs ^a), or more frequently if clinically indicated, until total bilirubin has returned to baseline or stabilized over 4 weeks.
Isolated AST or ALT elevation	
> ULN - 3.0 x ULN	Maintain dose level
> 3.0 - 5.0 x ULN	Maintain dose level. Repeat LFTs ^a as soon as possible, preferably within 48-72 hours from awareness of the abnormal results; if abnormal lab values are confirmed upon the repeat test, then monitor LFTs ^a weekly, or more frequently if clinically indicated, until resolved to $\leq 3.0 \times$ ULN
> 5.0 - 10.0 x ULN	Interrupt study drug. Repeat LFTs ^a as soon as possible, preferably within 48-72 hours from awareness of the abnormal results; monitor LFTs ^a weekly, or more frequently if clinically indicated, until resolved to $\leq 3.0 \times$ ULN. Then: If resolved in ≤ 14 days, restart study drug and maintain dose level If resolved in > 14 days, restart study drug and decrease dose by one level If not resolved after 4 weeks, discontinue patient from study drug
> 10.0 - 20.0 x ULN	Interrupt study drug. Repeat LFTs ^a as soon as possible, preferably within 48-72 hours from awareness of the abnormal results; monitor LFTs ^a weekly, or more frequently if clinically indicated, until resolved to $\leq 3 \times$ ULN. Then restart study drug and decrease dose by one level. If not resolved after 4 weeks, discontinue patient from study drug
> 20.0 x ULN	Discontinue patient from study drug treatment. Repeat LFTs ^a as soon as possible, preferably within 48-72 hours from awareness of the abnormal results; monitor LFTs ^a weekly, or more frequently if clinically indicated, until returned to baseline or stabilized over 4 weeks.
Combined ^{b, c} elevations of AST or ALT and total bilirubin	
For patients with normal baseline ALT and AST and total bilirubin value: AST or ALT $>3.0 \times$ ULN combined with total bilirubin $>2.0 \times$ ULN without evidence of cholestasis ^c OR For patients with elevated baseline AST or ALT or total bilirubin value: [AST or ALT $>2x$ baseline AND $> 3.0 \times$ ULN] OR [AST or ALT $> 8.0 \times$ ULN], combined with [total bilirubin $>2x$ baseline AND $>2.0 \times$ ULN	Permanently discontinue patient from study drug treatment. Repeat as soon as possible, preferably within 48 hours from awareness of the abnormal results, then with weekly monitoring of LFTs ^a), or more frequently if clinically indicated, until AST, ALT, or bilirubin have returned to baseline or stabilized over 4 weeks. Refer to Section 6.3.3.1 for additional follow-up evaluations as applicable.

All dose modifications should be based on the worst preceding toxicity.

- a. Core LFTs consist of ALT, AST, GGT, total bilirubin (fractionated [direct and indirect], if total bilirubin > 2.0 x ULN), and alkaline phosphatase (fractionated [quantification of isoforms], if alkaline phosphatase > 2.0 x ULN.)
- b. "Combined" defined as: total bilirubin increase to the defined threshold concurrently with ALT/AST increase to the defined threshold.

If combined elevations of AST or ALT and total bilirubin do not meet the defined thresholds, please follow the instructions for isolated elevation of total bilirubin and isolated elevation of AST/ALT, and take a conservative action based on the degree of the elevations (e.g. discontinue study drug at the situation when interrupt study drug is needed for one parameter and discontinue study drug is required for another parameter). After all elevations resolve to the defined thresholds that allow treatment re-initiation, re-start the treatment either at the same dose or at one dose lower if meeting a criterion for dose reduction

- c. "Cholestasis" defined as: ALP elevation (>2xULN and R value (ALT/ALP in x ULN) < 2).

Note: The R value is calculated by dividing the ALT by the ALP, using multiples of the ULN for both values.

It denotes whether the relative pattern of ALT and/or ALP elevation is due to cholestatic ($R \leq 2$), hepatocellular ($R \geq 5$), or mixed ($R > 2$ and < 5) liver injury

* Note: If total bilirubin > 3.0 x ULN is due to the indirect (non-conjugated) component only, and hemolysis as the etiology has been ruled out as per institutional guidelines (e.g., review of peripheral blood smear and haptoglobin determination), then ↓ 1 dose level and continue treatment at the discretion of the investigator.

In addition, any AE per investigator judgment, regardless of suspected drug causality, may require interruption of study drug and replacement therapy with glucocorticoids until improvement of the event. These events, associated treatments along with changes to the dosing regimen of study drug need to be documented in the eCRF as soon as possible to enable the IE (up to Week 12) to make the appropriate dose decisions.

If the patient has interruption of study drug for more than 4 weeks, the investigator should consider early discontinuation from the study drug. Patients who had interruption of study drug and mUFC remains \leq ULN off study drug should remain on study.

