The investigator must discontinue study drug for a given patient if he/she believes that continuation would be detrimental to the patient's well-being. The investigator must also contact the IRT to register the patient's discontinuation from study drug.

Patients must discontinue study drug if any of the following occur:

- Emergence of the following adverse events:
- hypertension defined as office mean supine systolic BP > 180 mmHg or mean supine diastolic BP > 110 mmHg (confirmed and persistent*).
- Any of the following laboratory abnormalities (confirmed):
 - hyperkalemia (serum potassium > 6.0 mmol/L).
 - hypokalemia (serum potassium < 2.8 mmol/L).
- Any of the following laboratory abnormalities (confirmed and persistent*):
 - hyperkalemia (serum potassium > 5.5 mmol/L).
 - hypokalemia (serum potassium < 3.0 mmol/L).
 - hyponatremia (serum sodium < 130 mmol/L).
 - hyperglycemia (fasting plasma glucose \geq 15.0 mmol/L).

* Persistent is defined as unresolved with osilodrostat dose change or after adjustments to other concomitant medications targeting the co-morbidity in question.

- Abnormal liver function as described in [Table 6-2](#).
- Mean QTcF > 500 msec, if the QTc value is confirmed by a cardiologist (see [Section 7.2.2.7](#)).

- Mean QTcF > 480 msec, if the investigator determines it is no longer safe for the patient to continue in the study, based on ECGs, cardiac examination, and recommendation from a cardiologist (see [Section 7.2.2.7](#)).
- Mean increase in QTcF > 30 msec from the mean baseline value at 1.5h post-first dose or the QTcF is > 480 msec at Day 1.
- QTcF increase > 60 msec from the pre-dose measurement earlier during the same visit.
- Pituitary tumor growth, if symptomatic or complicated by compression of the optic chiasm or other structures in and near the sella turcica (visual field loss, cranial nerve palsies, diplopia) and confirmed by MRI of the pituitary (see [Section 7.2.2.5](#)).
- Pregnancy.
- Use of prohibited treatment (refer to [Section 6.4.3](#)).
- Any other protocol deviation that results in a significant risk to the patient's safety.

The appropriate personnel from the site and Novartis will assess whether study drug should be discontinued for any patient whose treatment code has been broken inadvertently for any reason.

The investigator must also contact the IRT to register the patient's discontinuation from study drug within 2 days.

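### Table 6-2 handles an indirect-only bilirubin rise (hemolysis ruled out) more strictly at 2 x ULN than at 5 or 12 x ULN, and in Period 1 its one-level decrease conflicts with Section 6.2.1.3 for placebo patients on 2 mg b.i.d. with mUFC >= 1.5 x ULN

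*Protocol*

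**What the plan says.** **Bilirubin rows (Protocol 6.3.1, Table 6-2).** For isolated total bilirubin above 1.5 and up to 3.0 x ULN the instruction is "Interrupt study drug dose. Monitor LFTs weekly, or more frequently if clinically indicated, until resolved to" 1.5 x ULN or less. Restart is at the same dose if this takes up to 14 days, and one level lower if it takes longer. This row has no asterisk. The next row, "> 3.0 - 10.0 x ULN", and the row above 10.0 x ULN both have one. Without the footnote, the first of these means interruption (discontinuation if not resolved within 14 days) and the second means discontinuation.

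**Asterisk footnote.** Its condition is "If total bilirubin > 3.0 x ULN is due to the indirect (non-conjugated) component only", with hemolysis excluded as the cause. Its action is to go down "1 dose level and continue treatment at the discretion of the investigator". No upper limit is given.

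**Discontinuation list (Protocol 7.1.4).** It includes "Abnormal liver function as described in" Table 6-2 and sets no liver threshold of its own.

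**One-level decrease.** Several Table 6-2 rows order it, for example AST or ALT above 10.0 and up to 20.0 x ULN once resolved: "Then restart study drug and decrease dose by one level". The table speaks of study drug, which the glossary defines as osilodrostat or placebo.

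**Limit for placebo patients (Protocol 6.2.1.3).** In Period 1, "only placebo-treated patients with mUFC < 1.5 x ULN will be down-titrated to doses below 2 mg b.i.d". The stated reasons are to avoid unblinding and to avoid prolonged hypercortisolism after Week 12.

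**The concern.** A dose-change table should give one action for each value, and a reader expects the action to follow the size of the abnormality unless a reason is stated. Here an indirect-only rise meets an unconditional interruption in the lower band and a conditional route to stay on drug in the higher bands. An investigator applying the table literally would hold drug at 2 x ULN and could keep a comparable patient on a reduced dose at 5 or 12 x ULN.

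The second conflict concerns the blind. Bilirubin and transaminases are not among the results withheld from sites in Period 1 (Protocol 4.1 and 6.5.3), so a site can see when Table 6-2 calls for a decrease. If the dosing system returns none, a site that knows 6.2.1.3 has a clue that the patient is on placebo. If the decrease is made, the patient starts Period 2 on active drug at that low dose (Protocol 4.1), which 6.2.1.3 was written to avoid.

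**Working it through.** The plan states no figure on this point, so there is nothing to reproduce. The check is a walk through the rules plus one illustrative calculation.

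**Step 1. Table 6-2 as a lookup, isolated total bilirubin.**

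| Total bilirubin (x ULN) | Not indirect-only | Indirect-only, hemolysis ruled out |
|---|---|---|
| 1.4 | maintain | maintain |
| 1.6, 2, 2.5, 3.0 | interrupt until <= 1.5 | interrupt until <= 1.5 |
| 3.1, 5, 10 | interrupt until <= 1.5; discontinue if over 14 days | one level down, continue at discretion |
| 10.1, 12 | discontinue | one level down, continue at discretion |

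The middle column escalates throughout. The right-hand column moves from interruption to reduced-dose continuation on crossing 3.0 x ULN. Missing information does not explain the step: direct and indirect bilirubin are in the routine chemistry panel (Protocol Table 7-4), and Table 6-2 footnote a calls for fractionation above 2.0 x ULN, inside the band without an exception. A patient improving from 5 to 2.5 x ULN moves from a row where drug may continue to one where it is interrupted; the table's rule to go by the worst preceding toxicity does not clearly settle which row governs.

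**Step 2. Table 6-2 against Section 6.2.1.3.** Period 1 starts at 2 mg b.i.d., the lowest of the standard doses 2, 5, 10 and 20 mg b.i.d. The doses named below it in Protocol 2.3 are 1 mg b.i.d., 1 mg q.d. and 1 mg every other day. One level down from 2 mg b.i.d. is therefore below 2 mg b.i.d. For a placebo patient with mUFC >= 1.5 x ULN, Table 6-2 orders that step and 6.2.1.3 excludes it. Both cannot be followed.

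**Step 3. What share of placebo patients has mUFC >= 1.5 x ULN?** The documents give no mUFC distribution. Entry requires mUFC > 1.3 x ULN, and the sample-size section assumes 15% of placebo patients at or below ULN at Week 12. As an illustration, assume a lognormal distribution with 15% at or below 1.0 x ULN and median m:

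- sigma = ln(m) / 1.036
- share = 1 - Phi[(ln 1.5 - ln m) / sigma]

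For m = 2: sigma = 0.693 / 1.036 = 0.669; (0.405 - 0.693) / 0.669 = -0.43; share = 67%.

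| Assumed median (x ULN) | 1.3 | 1.5 | 1.75 | 2 | 3 | 4 | 7 |
|---|---|---|---|---|---|---|---|
| Share >= 1.5 x ULN | 29% | 50% | 61% | 67% | 74% | 77% | 79% |

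Of 23 planned placebo patients this is 0.29 x 23 = 7 to 0.79 x 23 = 18. The conflict also requires 2 mg b.i.d. at the time and a qualifying liver event, for which no rate is given.

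**Step 4. Timing.** The Amendment 2 rationale says that on 10 December 2019 the study was fully enrolled and that the last patient should reach Week 48 by the end of February 2020. That is at most 21 + 31 + 29 = 81 days, or 11.6 weeks, later. The last patient was thus at about Week 48 - 11.6 = 36, well past Week 12.

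**The case against.** **On bilirubin.** The strongest reply is that a non-hemolytic, indirect-only rise may deserve its own pathway, and that the footnote is guarded: hemolysis excluded, dose reduced, investigator's discretion. A patient at 2 x ULN whose value settles within 14 days even returns to full dose. This stands as a limit on the point: only the indirect-only pathway is affected, and the AST/ALT rows and the other bilirubin rows escalate normally. It does not explain why the pathway is closed at 1.5 to 3.0 x ULN to a patient who meets the same conditions.

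**Above 10 x ULN.** A reader might infer that the footnote contradicts both its own row and a mandatory stop in 7.1.4. It does not. The asterisk is printed on that row, so the footnote is an express exception, and 7.1.4 refers back to Table 6-2, footnote included.

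**On the placebo limit.** One can argue that 6.2.1.3 governs titration and not toxicity, or that the exemption for urgent safety changes lifts it. But the stated reasons in 6.2.1.3 apply whatever prompts the low dose, and the exemption closes Section 6.2.1.4, where it qualifies the timing of dose changes. Neither reading is written down. It is also fair that simulated up-titration moves placebo patients off 2 mg b.i.d., and that a new instruction can no longer protect the Period 1 blind.

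**On the primary endpoint.** A reader might infer that patients with a stable mild elevation are pushed into non-response. The documents do not support this. Entry excludes values above 1.5 x ULN, and values up to 1.5 x ULN keep their dose. The core-phase SAP (2.5.1) lets temporary safety interruptions stand without loss of responder status, and after 4 weeks of interruption discontinuation is only to be considered. Discontinuation before Week 12 does count as non-response, but no route to a material effect is shown.

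**Conclusion.** Two conflicts stand as written. First, for an indirect-only bilirubin rise with hemolysis ruled out, Table 6-2 is stricter at 1.5 to 3.0 x ULN than at any value above 3.0 x ULN. Second, in Period 1, Table 6-2 and Section 6.2.1.3 cannot both be followed for a placebo patient on 2 mg b.i.d. with mUFC >= 1.5 x ULN who meets a row ordering a one-level decrease; a decrease not made could hint at treatment assignment.

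The size is small. The number of patients is not in the documents and is assumed low. It is tempting to say that the second conflict covers most placebo patients, but that needs an assumed median mUFC above 1.5 x ULN; the illustrative range is 29% to 79%, before requiring a liver event. No effect on the Week 12 endpoint is shown. The bilirubin rule applies in every phase and so still concerned the 45 patients on treatment on 10 December 2019; the placebo conflict by then concerned no one still in Period 1.

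**What to change.** Reconcile the Table 6-2 bilirubin rows with the indirect-bilirubin footnote, so that each value has one consistent action and it is clear which row governs a falling value. Reconcile the one-level decrease in Table 6-2 with the 1.5 x ULN limit in Section 6.2.1.3, stating which takes precedence for blinded patients on 2 mg b.i.d. Which action applies in each case is for the sponsor's medical team; this review takes no position.

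The cost is wording in an amendment or investigator letter. Fractionated bilirubin is already in the central panel. Whether further tests are needed depends on the choice made: the hemolysis work-up named in the footnote includes haptoglobin, which is not listed in Table 7-4. For the placebo conflict, the change now serves the record and any later protocol that reuses this table.
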